12.15.2 Chemistry

Serum chemistry consists of a peripheral blood draw with the following assessments: sodium, potassium, blood urea nitrogen (BUN) or urea, fasting glucose, albumin, creatinine, total cholesterol, triglycerides, total bilirubin (direct and indirect, only if total bilirubin is out normal range), GOT, GPT, GGT, alkaline phosphatase, LDH, magnesium, phosphorous and calcium. Amylase and lipase determinations will be added only in screening and during bosutinib plus atezolizumab combination treatment.

The chemistry assessments must be obtained at:

- Screening
- During first therapy (before treatment):
 - Day 1 of cycle 1 (visit 1/D1).
- During second therapy (before treatment):
 - Day 1 of cycle 2. Before the patient takes the bosutinib plus atezolizumab combination for first time.
 - Day 1 of cycles 4, 7, 10, and 13.

- During third therapy:
 - Day 1 of cycle 14. Before the patient takes bosutinib 400 mg/day in monotherapy, for the first time again for the treatment of CML.
 - Day 1 of cycle 20.
 - At the End of Treatment: Day 29 (Last dose) of cycle 25.
 - At the End of Study, (visit EOS or follow up): 28 days after the last dose.

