11.6.2.4 Endocrine Events

Thyroid disorders, type 1 diabetes mellitus, adrenal insufficiency, and pituitary disorders have been associated with the administration of atezolizumab.

Subjects with unexplained symptoms such as fatigue, myalgias, impotence, constipation, or mental status changes, should be investigated for the presence of thyroid, pituitary, or adrenal endocrinopathies. An endocrinologist should be consulted if an endocrinopathy is suspected. Thyroid stimulating hormone (TSH), triiodothyronine 3 (T3), and free thyroxine (T4) levels should be obtained to determine whether thyroid abnormalities are present. Pituitary hormone levels and function tests (e.g., TSH, growth hormone, luteinizing hormone, follicle-stimulating hormone, testosterone, prolactin, adrenocorticotrophic hormone [ACTH] levels and ACTH stimulation test) and MRI of the brain (with detailed pituitary sections) may help to differentiate primary adrenal insufficiency from primary pituitary insufficiency.

For specific management guidelines, please see Table 6.

Table 6. Management Guidelines for Endocrine Events

Adverse Event	Management
Asymptomatic hypothyroidism	
▪ Continue atezolizumab.▪ Initiate treatment with thyroid replacement hormone.▪ Monitor TSH weekly.
Symptomatic	
▪ Withhold atezolizumab.▪ Initiate treatment with thyroid replacement hormone.

Adverse Event	Management
hypothyroidism	
Monitor TSH weekly.Consider subject referral to endocrinologist.Resume atezolizumab when symptoms are controlled and thyroid function is improving.
Asymptomatic hyperthyroidism	
TSH \geq0.1 mU/L and $<$0.5 mU/L:
 
Continue atezolizumab.Monitor TSH every 4 weeks. 
TSH $<$0.1 mU/L:
 
Follow guidelines for symptomatic hyperthyroidism.
Symptomatic hyperthyroidism	
Withhold atezolizumab.Initiate treatment with anti-thyroid drug such as methimazole or carbimazole as needed.Consider subject referral to endocrinologist.Resume atezolizumab when symptoms are controlled and thyroid function is improving.Permanently discontinue atezolizumab and contact the Sponsor for life-threatening immune-related hyperthyroidism.^a

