11.6.2.7 Pancreatic Events

Symptoms of abdominal pain associated with elevations of amylase and lipase, suggestive of pancreatitis, have been associated with the administration of atezolizumab. The differential diagnosis of acute abdominal pain should include pancreatitis. Appropriate work-up should

include an evaluation for ductal obstruction, as well as serum amylase and lipase tests. For specific management guidelines please see Table 9.

Table 9. Management Guidelines for Pancreatic Events, Including Pancreatitis

Adverse Event	Management
Amylase and/or lipase elevation, Grade 2	
▪ Continue atezolizumab.▪ Monitor amylase and lipase weekly.▪ For prolonged elevation (e.g., >3 weeks), consider treatment with 10 mg/day oral prednisone or equivalent.
Amylase and/or lipase elevation, Grade 3 or 4	
▪ Withhold atezolizumab for up to 12 weeks after event onset.^a▪ Refer subject to gastrointestinal specialist.▪ Monitor amylase and lipase every other day.▪ If no improvement, consider treatment with 1-2 mg/kg/day oral prednisone or equivalent.▪ If event resolves to Grade 1 or better, resume atezolizumab.^b▪ If event does not resolve to Grade 1 or better while withholding atezolizumab, permanently discontinue atezolizumab and contact Sponsor.^c▪ For recurrent events, permanently discontinue atezolizumab and contact the Sponsor.^c
Immune-related pancreatitis, Grade 2 or 3	
▪ Withhold atezolizumab for up to 12 weeks after event onset.^a▪ Refer subject to gastrointestinal specialist.▪ Initiate treatment with 1-2 mg/kg/day intravenous methylprednisolone or equivalent and convert to 1-2 mg/kg/day oral prednisone or equivalent upon improvement.▪ If event resolves to Grade 1 or better, resume atezolizumab.^b▪ If event does not resolve to Grade 1 or better while withholding atezolizumab, permanently discontinue atezolizumab and contact Sponsor.^c▪ For recurrent events, permanently discontinue atezolizumab and contact the Sponsor.^c

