12.15 Laboratory Evaluations

Local laboratories will be used for analysis of hematology specimens collected and for analysis of biochemistry and serology specimens collected.

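### Table 6 orders action on symptom-free thyroid abnormalities, but no scheduled blood draw measures TSH, so these cases are not systematically found and have no baseline for comparison

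*Protocol*

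**What the plan says.** **What is measured.** Protocol 12.15.2 defines the panel: "Serum chemistry consists of a peripheral blood draw with the following assessments: sodium, potassium, blood urea nitrogen (BUN) or urea, fasting glucose, albumin, creatinine", followed by lipids, bilirubin, liver enzymes, LDH and minerals. One addition is tied to the combination: "Amylase and lipase determinations will be added only in screening and during bosutinib plus atezolizumab combination treatment". No thyroid test appears there, in Tables 14 to 17, or in the SAP 6.3 baseline list.

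**What triggers a thyroid test.** Section 11.6.2.4 acknowledges that atezolizumab is associated with thyroid disorders and then makes work-up symptom-led: "Subjects with unexplained symptoms such as fatigue, myalgias, impotence, constipation, or mental status changes, should be investigated for the presence of thyroid" and other endocrine disorders.

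**What Table 6 requires.**
- The row "Asymptomatic hypothyroidism" continues atezolizumab, starts thyroid replacement and asks for weekly TSH.
- Asymptomatic hyperthyroidism is split by TSH. From 0.1 to below 0.5 mU/L, atezolizumab continues and TSH is checked every 4 weeks. Below 0.1 mU/L the instruction is "Follow guidelines for symptomatic hyperthyroidism", and that row withholds the drug.
- The condition for restarting is "Resume atezolizumab when symptoms are controlled and thyroid function is improving". No re-test interval is given.

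**How safety is analysed.** Safety is the primary objective. Protocol 15.3.2 and SAP 6.9 summarise adverse events that are new or worse relative to baseline. Protocol 15.3.3 and SAP 6.9 plan shift tables from baseline to the worst on-treatment value.

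**The concern.** In a patient without symptoms, only a blood test can show the states that Table 6 acts on. The schedule never orders that test, so a site can follow the plan exactly and still miss patients whom the plan says to treat, monitor or hold.

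Two things are at stake. The first is patient safety, including the TSH level at which the protocol withholds atezolizumab. The second is the primary safety description: reported thyroid incidence will depend partly on who happened to be tested, and a subclinical finding will have no baseline to be compared with.

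**Working it through.** No figure in the plan needs reproducing; the check is a count and a comparison of sections.

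**1. Scheduled draws (12.15.2, cross-checked against Tables 14 to 17).** Screening, C1 D1 (D1), C2 D1 (D29), C4 (D85), C7 (D169), C10 (D253), C13 (D337), C14 (D365), C20 (D533), EOT (D700) and EOS (D728) make 11. By table, 7 + 4 = 11 for each group. The panel has 19 named analytes including amylase and lipase. None is a thyroid test, so thyroid function is measured at 0 of 11 draws.

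**2. Comparison with the pancreas.** Table 9 acts on a laboratory finding, "Amylase and/or lipase elevation, Grade 2", and amylase and lipase were put into the panel for screening and the combination period. Table 6 acts on TSH, and TSH was not added.

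**3. Coverage after the fix.** Nine of the 11 draws would carry TSH: screening, D29, D85, D169, D253, D337, D365, D533 and D700. The first two precede the first atezolizumab dose. Gaps from D29 to D365 are 56, 84, 84, 84 and 28 days; then D365 to D533 is 168 days and D533 to D700 is 167. Omitting C20 would leave 700 − 365 = 335 days without a TSH.

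**4. Scheduled assays.** Each patient who completes needs 9. If all 36 are assayed at screening and 30 to 31 enter the combination and complete (the assumption in protocol 15.5), the count is 36 + 30 × 8 = 276 to 36 + 31 × 8 = 284. If all 36 complete, it is 36 × 9 = 324. Screen failures, early-termination visits, reflex free T4 and follow-up TSH come on top, so none of these is a ceiling.

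**5. Would a hold run into the withdrawal rule?** Sections 9.5 and 11.6 allow 3 missed atezolizumab doses and withdraw the patient at 4. Take a 1680 mg q4w hold triggered by the D85 draw, with thyroid function improving by the D169 draw:
- Results available before infusion: D85, D113 and D141 are missed and D169 is given. That is 3 missed.
- Results available only after the visit: D85 is given, D113, D141 and D169 are missed, and D197 is given. That is again 3 missed.

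Under 840 mg q2w dosing, the fourth missed dose comes 3 × 14 = 42 days after the first, before a next scheduled TSH that is 56 or 84 days away. A 4-weekly re-test gives one result, at day 28, before that dose.

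**The case against.** The strongest reply is that Table 6 tells sites how to manage whatever is found and need not imply screening. Table 3 likewise asks for serial imaging that Tables 14 to 17 do not schedule. The symptom trigger is broad, physical examinations include the thyroid (12.12), known disease is captured by history and prior medication (12.5, 12.6), active autoimmune disease needing treatment is excluded (criterion 15), and a test result that changes dosing or treatment is reportable (13.2). Thyroid events are not on the protocol's list of events of special interest.

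Much of this stands: overt or known thyroid disease will be captured, and the gap is confined to symptom-free patients. It does not close that gap. Imaging in Table 3 follows an event already recognised, whereas the asymptomatic rows of Table 6 cannot be reached without a TSH result. Examining the neck does not measure TSH. Exceptions to the dose-modification guidance need Medical Monitor approval (11.6), so Table 6 is not optional.

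A reader might infer three stronger points, which the documents do not support:
- *That such findings cannot be counted as treatment-emergent.* Protocol 15.3.2 includes events that start during treatment, so an abnormality first found then can be recorded by onset date. What is lost is evidence that it is new, and the baseline shift.
- *That a re-test rule is essential on q4w dosing.* Step 5 gives 3 missed doses under either consistent laboratory turnaround. Reaching 4 requires same-day results at one draw and delayed results at the next. Table 6 already ties restarting to improving thyroid function, so the missing interval is minor.
- *That the dose-limiting toxicity decision or a comparison is biased.* The non-haematological criterion in 9.3.1 centres on clinically evident Grade 3 or 4 toxicity, and the study has no concurrent control.

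**Conclusion.** The point holds in limited form. Thyroid function is measured at 0 of 11 scheduled draws, while Table 6 requires treatment, monitoring or a hold in symptom-free patients on thyroid test results. Following the plan as written does not systematically find them. A subclinical abnormality found on study cannot be shown to be new rather than pre-existing, and no shift from baseline can be tabulated for it.

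This rests on reading Table 6 as binding and on sites testing only what is scheduled or clinically prompted; a site that checks TSH routinely would narrow the gap locally but make detection uneven across sites. No number of missed cases is claimed, because the documents give no thyroid event rate. No effect on the dose-limiting toxicity decision and no between-arm bias is claimed. The change is worth making because the blood is already drawn and safety is the primary objective.

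**What to change.** **Main change.**
- In 12.15.2 and Tables 14 to 17, add TSH, with free T4 if TSH is abnormal, to the chemistry sample at screening, C2 D1 (before the first atezolizumab dose), C4, C7, C10, C13, C14, C20 and EOT.
- Name TSH in the SAP 6.3 baseline list and the SAP 6.9 laboratory shift tables. The existing low/normal/high rule for tests without CTCAE grades can be used.
- Report how many atezolizumab holds were triggered by TSH alone.

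**Optional and minor.** State a TSH re-test every 4 weeks while atezolizumab is held for TSH below 0.1 mU/L. This can shorten holds and matters for the withdrawal rule mainly under q2w dosing.

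**Cost.** A protocol amendment and a SAP edit, plus the assays in step 4. No new laboratory arrangement is needed: "Local laboratories will be used for analysis of hematology specimens collected and for analysis of biochemistry and serology specimens collected". Weekly TSH in hypothyroidism needs extra draws. Four-weekly checks fit existing Day 1 combination visits, but those without chemistry (C3, C5, C6, C8, C9, C11, C12) need a sample. Some symptom-free patients will have doses held that would otherwise be given, and those count toward the four-missed-dose rule. Because the full analysis set contains only patients who complete the combination, one resulting withdrawal would remove 1/31 = 3.2% to 1/30 = 3.3% of it, if otherwise all 30 to 31 would complete. Asymptomatic hypothyroidism and TSH from 0.1 to below 0.5 mU/L do not trigger a hold.

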12.15.3 Serology

At the time of screening, blood serum must be tested for Hepatitis B serology (Hepatitis B surface antigen, Hepatitis B core antibody, and Hepatitis B surface antibody) hepatitis C and HIV, in all patients.

12.16 Bone Marrow Analysis and Cytogenetics

Bone marrow aspiration will be performed at screening and every three months until Complete Cytogenetic Response (CCyR) is reached or after suspected disease progression.

Cytogenetic response will be assessed as the percentage of Ph+ metaphases in the bone marrow and is defined as the following (a review of a minimum of 20 metaphases is convenient):

- Complete (CCyR) 0% Ph+ metaphases
- Partial (PCyR) - >0 to 35% Ph+ metaphases
- Minor (mCyR) - >35 to 65% Ph+ metaphases
- Minimal - >65 to 95% Ph+ metaphases
- None - >95 to 100% Ph+ metaphases

These exams will be performed and analyzed locally. Quantification of the percentage of Ph+ chromosome metaphases, number of metaphases, number of positive for Ph chromosome, additional chromosomal abnormalities, if applicable, will be collected.

Fluorescent In-situ hybridization (FISH) analysis will not be accepted. If the sample cannot be quantified, the extraction must be repeated as soon as possible.

12.17 Pregnancy Test

The pregnancy test must be a beta-human chorionic gonadotropin (β -HCG) test, using either urine or serum. Women who are not of childbearing potential (status post- hysterectomy, status post-bilateral oophorectomy, or postmenopausal [defined as amenorrhea for at least 12 months]) do not need to have the test performed. If the test is deemed necessary, it must be performed in screening visit or during visit 1 before the first dose of study drug and known to be negative prior to drug administration. Women of childbearing potential at study start must also complete the pregnancy test each month during the study, at the end-of-treatment visit and at the end-of-study visit.

12.18 Inmunological Studies

Samples: whole blood (30 ml in EDTA tubes) from all patients treated with bosutinib.

Maximum number of samples per patient: 6 (180 ml of blood in total in two years).

Blood samples for exploratory immunological and virological analysis will be measured at:

- Screening
- During second therapy (before treatment):
 - Day 1 of cycle 2. Before the patient takes the bosutinib plus atezolizumab combination for first time.
 - Day 1 of cycle 13.
- During third therapy:
 - Day 1 of cycle 14. Before the patient takes bosutinib 400 mg/day in monotherapy, for the first time again for the treatment of CML.
 - At the End of Treatment: Day 29 (Last dose) of cycle 25.
 - At the End of Study, (visit EOS or follow up): 28 days after the last dose.

12.19 Adverse Events and Concomitant Medications

AEs and concomitant medications will be recorded continuously throughout the study, starting on the date of the first administration of the study medication, and, at least, up to the 28-day follow-up visit after the last dose of treatment. New and updated AEs and concomitant medications will be reported within the treatment period; ongoing AEs thought to be at least possibly study-drug related; and all ongoing SAEs should be followed at least every 4 weeks until they resolve to baseline (or to NCI CTCAE, v5.0 grade ≤ 1), stabilize, or are considered to be chronic/irreversible (see section 13 Adverse Events reporting, for more information). Those relevant events that start before the first administration of the study drug will be recorded in the clinical history of the subject.

A maximum discontinuation of 1 month is allowed for the treatment with bosutinib if required due to the onset of adverse events, investigator decision, or other major circumstances. If a subject discontinued treatment for more than one month he/she will be withdrawn from the study and the appropriate follow-up procedures will be conducted. Regarding atezolizumab treatment, fail to administrate up to 3 out of the 11 administrations scheduled will be allowed for a patient to continue in the study. If, for some reasons, atezolizumab could not be administered 4 or more times, during the course of the study, the subject will be withdrawn from the study and the appropriate follow-up procedures will be conducted. All deviations from the scheduled treatments regime shall be recorded in the patients' clinical history and the eCRF and explained if required.

12.20 End of Treatment or Early Termination Procedures

The end of treatment for the early termination visit should be performed within 2 weeks (14 days) of the patient's last dose of study drug or the patient/investigator decision to discontinue treatment. Survival information, stem cell transplantation, TKI therapy status, as well as information on the status of the patient's disease (i.e., disease progression to AP/BC according to protocol definition, or CML related death) will be collected, if applicable. The information may be collected from tests that were performed for the study or as part of the patient's routine medical care.

Patients that finished the study as per protocol will continue to receive treatment for CML, according to standard clinical practice. For those patients who withdraw before the end of the study, their physician will decide the best course of treatment indicated, following the standard clinical practice and current guidelines for the treatment of CML.

12.21 End of Study. Follow-up Safety Procedures

All AEs ongoing or starting within 28 days after end of treatment must be recorded in the eCRF. After this time, ongoing AEs thought to be at least possibly study-drug related, as well as all ongoing SAEs, should be followed at least every 4 weeks until they resolve to baseline (or to NCI CTCAE, v5.0 grade ≤ 1), stabilize, or are considered to be chronic/irreversible.

12.22 Biological Samples Treatment after the End of the Study

During the clinical trial, the management of biological samples will be carried out in accordance with the following:

The blood samples for the evaluation of the BCR-ABL transcript will be analyzed by the molecular biology hematology laboratory of the Doce de Octubre University Hospital, which since 2009 has the UNE-EN ISO9001: 2008 certification and since 2017: accredited by the UNE standard -EN ISO 15189: 2013, complying with all security and confidentiality regulations.

The samples for the immunological study will be analyzed by the AIDS Immunopathology Unit of the National Center for Microbiology, complying with all safety and confidentiality regulations.

The samples will be shipped the same day of the extraction to the corresponding central laboratories; they will not be stored in the centers. The samples will be used exclusively for the analysis foreseen in the protocol, and the surpluses will be destroyed after its completion.

The provisions of Law 14/2007, of July 3, on Biomedical Research and Royal Decree 1716/2011, of November 18, which establishes the basic requirements for authorization and operation of Biobanks with Biomedical research purposes and the

treatment of biological samples of human origin, and the operation and organization of the National Registry of Biobanks for biomedical research is regulated.

13 ADVERSE EFFECTS REPORTING

13.1 AE Definition

An AE is any untoward medical occurrence in a trial subject to whom a medicinal product is administered and which does not necessarily have a causal relationship with this treatment. An AE can be any unfavorable and unintended sign (including an abnormal laboratory finding), symptom, or disease temporally associated with the use of a medicinal product, whether or not that sign, symptom, or disease is considered related to the medicinal product. Adverse event is any worsening of a pre-existing condition that is temporally associated or not with the use of the study drug.

The adverse events that occurs since the patient signs the ICF but before he/she takes the first bosutinib dose will be considered as part of the clinical history of the patient.

Adverse events (including lab abnormalities that constitute AEs) should be described using a diagnosis whenever possible, rather than individual underlying signs and symptoms. When a clear diagnosis cannot be identified, each sign or symptom should be reported as a separate AE.

Adverse events will be assessed according to the Common Terminology Criteria for Adverse Events (CTCAE) version 5.0.

AEs include:

- Clinically significant abnormal test findings
- Clinically significant changes in physical exam findings
- Other untoward medical events, regardless of their relationship to the study drug, such as injury, events that require surgery, accidents, or apparently unrelated illnesses
- Hypersensitivity

Additionally, AEs may include signs or symptoms resulting from:

- Drug overdose
- Drug withdrawal
- Drug abuse
- Drug misuse
- Drug interactions
- Drug dependency
- Product complaint

13.2 Abnormal Test Findings

The criteria for determining whether an abnormal objective test finding should be reported as an AE are as follows:

- Test result is associated with accompanying symptoms that are considered clinically significant in the opinion of the investigator.
- Test result requires additional diagnostic testing (other than merely repeating an abnormal test) or medical/surgical intervention.
- Test result leads to a change in study drug dosing or discontinuation from the study, significant additional concomitant drug treatment, or other therapy.
- Test result is considered to be clinically significant by the investigator or sponsor.

